3.1 Characteristics

This is an open-label, single arm pilot study of defibrotide given as prophylaxis to patients receiving a conditioned stem cell transplant for the purpose of preventing post-transplant microangiopathy.

3.2 Number of Subjects

25 patients are expected to be enrolled.

3.3 Eligibility Criteria

Patients must have baseline evaluations performed prior to the first dose of study drug and must meet all inclusion and exclusion criteria. In addition, each patient must be thoroughly informed about all aspects of the study, including the study visit schedule and required evaluations and all regulatory requirements for informed consent. The written informed consent must be obtained from the patient prior to enrollment. The following criteria apply to all patients enrolled onto the study unless otherwise specified.

3.3.1 Inclusion Criteria

1. Age 0-30 years of age
2. Life expectancy > 6 months
3. ECOG or Karnofsky Performance Status >40
4. Meets minimum organ function requirements per institutional SOC guiding clearance for autologous or allogeneic stem cell transplantation.
5. Patients must meet TMA High-Risk criteria
 - A. Patients undergoing tandem autologous transplant with thiotepa in one or more of the conditioning regimens.

OR:

- B. . Patients with at least 3 of the following characteristics:
 - a. >10 years of age
 - b. Non-Caucasian race/ Hispanic ethnicity
 - c. Undergoing haploidentical transplant
 - d. Minor ABO Mismatch
6. The effects of defibrotide on the developing human fetus are unknown. For this reason and because other therapeutic drugs used as a part of transplant are known to be teratogenic, women of child-bearing potential and men must agree to use adequate contraception: abstinence per institutional stem cell transplantation guidelines, for the duration of study participation and for a minimum of 2 weeks after last dose of study drug. Should a woman become pregnant or suspect she is pregnant while she or her partner is participating in this study, she should inform her treating physician immediately. Men treated or enrolled on this protocol must also agree to use adequate contraception prior to the study, for the duration of study participation, and 2 weeks after last dose of study drug.
7. Ability to understand a written informed consent document, and the willingness to sign it

3.3.2 Exclusion Criteria

1. Age >30 years
2. Life expectancy < 6 months
3. Known bleeding diathesis or bleeding risk deemed by the treating physician to be a contraindication to administration of anticoagulants.
4. Known hypersensitivity reaction to defibrotide
5. Any patient not meeting TMA High-Risk criteria as defined in section 1.3
6. Pregnant women are excluded from this study because they will be receiving teratogenic therapy as part of the stem cell transplant.

3.4 Duration of Therapy

In the absence of treatment delays due to adverse events, treatment should begin the day prior to initiation of conditioning and continue until Day +21 post-HSCT, or:

- Disease progression
- Inter-current illness that prevents further administration of treatment
- Unacceptable adverse event(s)
- Patients decides to withdraw from the study
- Significant patient non-compliance with protocol
- General or specific changes in the patients' condition render the patient unacceptable for further treatment in the judgment of the investigator.

3.5 Duration of Follow Up

Patients will be followed for 6 months post-HSCT, or until death, whichever occurs first. Patients removed from study for unacceptable treatment related adverse event(s) will be followed until resolution or stabilization of all treatment-related adverse events to Grade 2 or lower.

3.6 Study Timeline

Accrual is estimated to begin in Fall 2017 and continue through Fall 2019. Patients will be followed for safety and efficacy through Spring 2020.

3.6.1 Primary Completion

The study will reach primary completion 24 months from the time the study opens to accrual.

3.6.2 Study Completion

The study will reach study completion 30 months from the time the study opens to accrual.

4 Study Drugs

4.1 Description, Supply and Storage of Investigational Drugs

4.1.1 Investigational Drug #1

Defibrotide is available as a solution, Intravenous, as sodium [preservative free]: Defitelio: 200 mg/2.5 mL (2.5 mL). Refer to the package insert for complete information.

Classification:

Therapeutic Category: Antiplatelet Agent; Thrombolytic Agent

Mechanism of Action:

Defibrotide augments plasmin enzymatic activity to hydrolyze fibrin clots. It reduces endothelial cell (EC) activation and increases EC-mediated fibrinolysis by increasing tissue plasminogen activator and thrombomodulin expression, as well as by decreasing von Willebrand factor and plasminogen activator inhibitor-1 expression.

Metabolism:

Polynucleotides are metabolized via nucleases, nucleotidases, nucleosidases, deaminases, and phosphorylases to oligonucleotides, nucleotides, nucleosides, and then to the free 2'-deoxyribose sugar, purine and pyrimidine bases

Contraindications:

Known hypersensitivity to defibrotide or any component of the formulation; concomitant administration with systemic anticoagulant or fibrinolytic therapy

Availability:

FDA approved March 2016

Storage and handling

Store intact vials at 20°C to 25°C (68°F to 77°F); excursions permitted between 15°C to 30°C (59°F to 86°F). Solutions diluted for infusion in D5W or NS should be used within 4 hours if stored at room temperature or within 24 hours if refrigerated. Discard partially used vials. Side

Effects

Complete and updated adverse event information is available in the Investigational Drug Brochure and/or product package insert.

4.2 Drug Accountability

The Investigational Pharmacist will manage drug accountability records.

4.3 Drug Ordering

UCSF will obtain defibrotide directly from pharmaceutical company as study supply.

4.4 Packaging and Labeling of Study Drugs

Drugs will be packaged and labeled per UCSF institutional standards, adhering to applicable local and federal laws.

5 Treatment Plan**5.1 Dosage and Administration****Table 5.1 Regimen Description**

Study Drug	Premedication; precautions	Dose	Route	Schedule	Cycle Length
Defibrotide	None	6.25 mg/kg	IV over 2 hours	Q6h	Day prior to start of conditioning through Day +21 Post-HSCT

Treatment will be administered on an inpatient basis.

5.1.1 Dose Modifications and Dosing Delays Tables for Specific Adverse Events

Adverse Event: Bleeding or Hypersensitivity reaction

Grade of Event	Management
≤ Grade 1	No change in dose
Grade 2	Hold until ≤ Grade 1 Resume at same dose level
Grade 3	Discontinue therapy
Grade 4	Discontinue therapy

*Patients requiring a delay of > 2 weeks should go off protocol therapy

5.2 Monitoring and Toxicity Management

Each patient receiving defibrotide will be evaluable for safety. The safety parameters include all laboratory tests and hematological abnormalities, physical findings, and spontaneous reports of adverse events reported to the investigator by patients.

Each patient will be assessed periodically for the development of any toxicity as outlined in [Section 6 Study Procedures and Observations](#). Toxicity will be assessed according to the NCI [CTCAE v4.0](#). Dose adjustments will be made according to the system showing the greatest degree of toxicity.

We will monitor for incidence of clinically significant bleeding and hypersensitivity reactions:

Hemorrhage: Defibrotide may increase the risk of bleeding (based on increased activity of fibrinolytic enzymes *in vitro*). **Do not initiate therapy in patients with active bleeding**; monitor closely for signs of bleeding. If hemodynamically significant bleeding develops while on therapy, discontinue defibrotide, evaluate/treat the underlying cause, and provide supportive care until bleeding resolves.

Hypersensitivity reactions: Hypersensitivity reactions (e.g., rash, urticaria, and angioedema) have been reported (rare). One patient with a history of previous defibrotide exposure experienced an anaphylactic reaction. Monitor closely for hypersensitivity reactions, particularly in patients who have received defibrotide previously. Discontinue therapy for severe hypersensitivity reactions and treat accordingly; monitor until symptoms resolve.

Acute toxicity will be managed by immediately stopping infusion of defibrotide and holding further doses. Hypersensitivity reactions will be managed per local protocols and standard of care. Further management will depend upon the judgment of the clinician.

5.2.1 Other toxicities:

The toxicities listed below have been reported in patients receiving defibrotide. None have been directly attributable to defibrotide itself.

Cardiovascular: Hypotension, thrombophlebitis

Central nervous system: Cerebral hemorrhage, intracranial hemorrhage

Endocrine & metabolic: Hot flash, hyperuricemia

Gastrointestinal: Abdominal cramps, abdominal pain, bloody diarrhea, diarrhea, gastrointestinal hemorrhage, hematemesis, nausea, vomiting

Genitourinary: Hematuria

Hematologic & oncologic: Hemorrhage, oral hemorrhage, pulmonary hemorrhage

Hypersensitivity: Hypersensitivity reaction

Immunologic: Graft versus host disease

Infection: Infection, sepsis

Renal: Renal failure

Respiratory: Epistaxis, pneumonia, pulmonary alveolar hemorrhage, pulmonary infiltrates

Miscellaneous: Fever

6 Study Procedures and Observations

6.1 Schedule of Procedures and Observations

The study-specific assessments are detailed in this section and outlined in Table 6.1, Schedule of Study Procedures and Assessments. Screening assessments must be performed within 28 days prior to the first dose of investigational product. Any results falling outside of the reference ranges may be repeated at the discretion of the investigator. All on-study visit procedures are allowed **a window of ± 2 days unless otherwise noted**. Treatment or visit delays for public holidays or weather conditions do not constitute a protocol violation.

A written, signed, informed consent form (ICF) and a Health Insurance Portability and Accountability Act (HIPAA) authorization must be obtained before any study-specific assessments are initiated. A copy of the signed ICF will be given to the subject and a copy will be filed in the medical record. The original will be kept on file with the study records.

All patients who are consented will be registered in the study database. The system is password protected and meets HIPAA requirements.

Patients undergoing tandem autologous transplants will repeat the schedule of procedures and assessments on admission for second transplant.

6.1.1 Pretreatment Period

6.1.1.1 Screening Assessments

The Screening procedures and assessments must be completed within 28 days prior to admission.

- Physical examination
- Vital signs
- Performance Status
- Patient and donor blood type, if eligible

6.1.2 Treatment Period

6.1.2.1 Study Procedures: Treatment (Day of admission through Day +21 post-HSCT)

These procedures must be completed weekly starting the day before the start of alkylating agents or TBI.

- Defibrotide 6.25mg/kg IV Q6h to start at 9 pm (+/- 3 hours) on the day prior to start of conditioning .
- Evaluation of clinical response or deterioration
- Physical examination
- Vital signs
- Performance Status
- Evaluation of adverse events
- Standard labs including
 - CBC with differential and platelet count, reticulocyte count
 - Blood chemistry assessment, including: alkaline phosphatase, ALT/AST, total bilirubin, calcium, phosphorus, magnesium, BUN, creatinine, total protein, albumin, fasting glucose, potassium, sodium, chloride, bicarbonate
 - Uric acid, LDH
 - Direct antiglobulin test, peripheral smear for RBC morphology,
 - Urine protein concentration, urine protein / creatinine ratio,
 - Complement activity (CH50)
 - Coagulation panel including PT/PTT, d-dimer

6.1.3 Post-treatment/Follow Up Visits

Patients will be followed *weekly until Day +28 then monthly* for up to 6 months after enrollment or until disease progression; exception for patients receiving tandem transplants will be followed *weekly until Day +28 then monthly* for up to 6 months after admission from second transplant or until disease progression. The following procedures will be performed at the Follow Up Visit(s):

- Evaluation of clinical response or deterioration
- Physical examination
- Vital signs
- Performance Status
- Evaluation of adverse events
- Standard labs including
 - CBC with differential and platelet count, reticulocyte count
 - Blood chemistry assessment, including: alkaline phosphatase, ALT/AST, total bilirubin, calcium, phosphorus, magnesium, BUN, creatinine, total protein, albumin, glucose, potassium, sodium, chloride, bicarbonate
 - Uric acid, LDH, haptoglobin
 - Direct antiglobulin test, peripheral smear for RBC morphology

- Urine protein concentration, urine protein / creatinine ratio
- Complement activity (CH50)
- Coagulation panel including PT/PTT, d-dimer

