5. I agree to maintain adequate and accurate records in accordance with CHR policies, Federal, state and local laws and regulations.

UCSF Principal Investigator / Study Chair

Printed Name

Signature

Date

Participating Site(s)

Telephone:
E-mail:

Telephone:
E-mail:

Telephone:
E-mail:

Principal Investigator

Site

Printed Name

Signature

Date

Abstract

Title	A Pilot Trial of Using Pre-Transplant Risk Stratification and Prophylactic Defibrotide to Prevent Serious Thrombotic Microangiopathy in High-Risk Hematopoietic Stem Cell Transplant Patients
Patient population	Pediatric patients age 0-30 years receiving autologous or allogeneic HSCT meeting TMA high risk criteria.
Rationale for Study	TMA is a common complication in the stem cell transplant population. Certain populations within the HSCT population are at a higher risk than others. Defibrotide is an endothelial stabilizing agent which may prevent the endothelial damage that triggers TMA in HSCT patients. The feasibility, safety, and efficacy of defibrotide prophylaxis in a pediatric transplant population is unknown.
Primary Objective	To determine the feasibility and safety of defibrotide in children receiving HSCT.
Secondary Objectives	To determine the efficacy of defibrotide prophylaxis in preventing severe TMA in pediatric patients receiving HSCT.
Study Design	Single arm non-randomized Phase II safety and feasibility trial of un-blinded defibrotide prophylaxis.
Number of patients	25
Duration of Therapy	Patients may continue treatment for 28-35 days from time of study drug initiation.
Duration of Follow up	Follow up for 6 months post-HSCT per HSCT standard of care.
Duration of study	The study will reach completion 30 months from the time the study opens to accrual.
Study Drugs	Defibrotide 6.25mg/kg IV Q6h for 28-35 days.
Safety Assessments	Weekly inpatient assessments of administration feasibility, hypersensitivity reaction, and bleeding while defibrotide is administered. This includes all HSCT SOC evaluations including routine clinical evaluations and laboratory assessments.
Efficacy Assessments	Efficacy will be based on overall incidence of TMA as well as incidence of severe TMA within 6 months post-HSCT, as defined in the protocol.

Unique Aspects of this Study	This is the first study to evaluate safety and efficacy of defibrotide in pediatric patients for prevention of severe TMA.
------------------------------	--

List of Abbreviations

AE	adverse event
ALP	alkaline phosphatase

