2.2 Secondary

- To determine if administration of prophylactic Defibrotide will prevent the development of TMA in clinically high-risk patients compared to historic controls.
 - Incidence of TMA in the first 6 months post-HSCT will be compared to incidence in a similar cohort of historical controls.
 - Incidence of severe TMA as defined by any TMA with the following complications:
 - Renal dysfunction requiring dialysis
 - Pleural or pericardial effusion requiring any medical or surgical intervention
 - CNS dysfunction including seizure, PRES
 - Death

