6.1.4 Discontinuation of Therapy

The Investigator will withdraw a patient whenever continued participation is no longer in the patient's best interests. Reasons for withdrawing a patient include, but are not limited to, disease progression, the occurrence of an adverse event or a concurrent illness, a patient's request to end participation, a patient's non-compliance or simply significant uncertainty on the part of the Investigator that continued participation is prudent. There may also be administrative reasons to terminate participation, such as concern about a patient's compliance with the prescribed treatment regimen

Table 6.1: Schedule of Study Procedures and Assessments⁴

	Screen	Days Pre-HSCT			Days Post-HSCT				Weeks Post-HSCT					TMA Dx
(+/- in days)	Admit (-28)	Admit	-7 (+/- 2)	-1 (+/- 1)	7 (+/- 2)	14 (+/- 2)	21 (+/- 2)	28 (+/- 2)	8 (+/- 7)	12 (+/- 7)	16 (+/- 7)	20 (+/- 7)	24 (+/- 7)	Dx (+/- 3)
Informed consent	X													
AE assessment		X	X	X	X	X	X	X	X	X	X	X	X	X
Defibrotide		X	X	X	X	X	X							+/-
Physical exam *		X	X	X	X	X	X	X	X	X	X	X	X	X
Vital signs *		X	X	X	X	X	X	X	X	X	X	X	X	X
Medical History *		X	X	X	X	X	X	X	X	X	X	X	X	X
Standard Labs ¹ *		X	X	X	X	X	X	X	X	X	X	X	X	X
Study Labs ²		X³		X	X		X							X

1. Labs per standard of care should include CBC, complete chemistry, LDH, uric acid, haptoglobin, direct antiglobulin test, peripheral smear for RBC morphology, urine protein concentration, urine protein / creatinine ratio, CH50, coagulation panel.
 2. Study labs to include plasma free Hgb, ST2, Ang-2, PAI-1, and hold specimen.
 3. +/- 2 day window
 4. Patients undergoing tandem autologous transplants will repeat the schedule of procedures and assessments on admission for second transplant, with the exception of screening.
- * Standard of care for patients undergoing HSCT

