8.4.4 Other analyses/Assessments

Other analysis include incidence of TMA by Day +30 post-HSCT, non-relapse mortality by Day +100 and by Day +180 post-HSCT. Summaries for biomarkers will be provided. Additional exploratory analyses may be performed based on incidence of elevation of single or combination of biomarkers predictive of development of TMA.

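### Section 6.1.3 can end TMA follow-up before 6 months post-HSCT or at progression, and the severe-TMA definition in 7.2.2 leaves out death, which section 2.2 and the historical 6/22 count

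*Combined protocol and SAP*

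**What the plan says.** **Follow-up.** Section 6.1.3 schedules visits "for up to 6 months after enrollment or until disease progression"; for tandem patients it is "for up to 6 months after admission from second transplant or until disease progression". The other places count from transplant:

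- Abstract: "Follow up for 6 months post-HSCT per HSCT standard of care".
- Section 2.2: "Incidence of TMA in the first 6 months post-HSCT will be compared to incidence in a similar cohort of historical controls".
- Section 3.5: "Patients will be followed for 6 months post-HSCT, or until death, whichever occurs first".
- Table 6.1: visits run to week 24 post-HSCT, ± 7 days.

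None of these four stops at progression. Section 6.1.4 adds: "Reasons for withdrawing a patient include, but are not limited to, disease progression". It does not say whether TMA is still ascertained after such a withdrawal.

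**Severe TMA.** Section 2.2 lists dialysis, effusion needing intervention, CNS dysfunction (naming seizure and PRES) and death. Section 7.2.2 lists dialysis, effusion needing intervention, CNS dysfunction (naming seizure only) and a TMA-related admission of more than 90 days; death is absent. Section 2.4.2 points to 7.2.2 as the endpoint definition. In the historical review in 1.3, a case was severe if it involved renal failure, pericardial effusion and/or death. That review supplies the 6 of 22 (27.3%) used as the comparator in 8.1.

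**The concern.** The secondary efficacy question is whether TMA and severe TMA are rarer than 7/22 and 6/22 in historical high-risk patients. That needs the same window for every trial patient, and the same case definition in the trial and the benchmark.

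A site that follows 6.1.3 literally stops looking for TMA early, on a day that depends on when the patient enrolled, or at once if the disease progresses. With all treated patients kept in the denominator (8.4.1), either cut-off can only miss cases.

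Under 7.2.2, a patient who dies with TMA and meets no other item on that list is not a severe case in the trial, but would have been one in the historical series. Section 8.1 also calls for re-evaluation at one severe case, so the same omission can decide whether that trigger fires. The primary safety and feasibility endpoints are not affected.

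**Working it through.** **1. Reproducing the plan's power figure.** Section 8.2.1 gives 92% power for 28% versus 4%, N=24, alpha 5%. An exact binomial test against a fixed 28% rejects at ≤2 of 24: P(X≤2 | 0.28) = 0.0196 and P(X≤3 | 0.28) = 0.064. Power is P(X≤2 | 0.04) = 0.931, close to the stated 92%. The plan does not name its test, so this is one plausible reading.

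**2. Length of the follow-up shortfall.** Inputs:

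- 6 months = 182.6 days.
- First dose to HSCT: 28–35 treatment days (Abstract) ending on Day +21 (3.4), so 28 − 21 = 7 to 35 − 21 = 14 days.
- Enrollment to first dose: the documents do not date enrollment. I assume 0–28 days, from the screening rule in 6.1: "Screening assessments must be performed within 28 days prior to the first dose of investigational product".

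Last day covered = 182.6 − (enrollment to first dose) − (first dose to HSCT):

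| Case | Calculation | Last day post-HSCT | Shortfall |
|---|---|---|---|
| Shortest lead | 182.6 − 0 − 7 | +175.6 | 7 days |
| Longest lead | 182.6 − 28 − 14 | +140.6 | 42 days |
| Tandem, from second admission | 182.6 − 7 to 182.6 − 14 | +175.6 to +168.6 | 7–14 days |

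The week-24 visit is nominally Day 168. It falls outside 6.1.3 once the total lead exceeds 182.6 − 168 = 14.6 days.

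**3. Cases missed by the calendar cut-off.** Section 1.3 says most cases were evolving before Day +100. Assume 10–30% arise later, spread evenly from Day +100 to Day +182.6 (82.6 days). Share lost = late share × shortfall / 82.6.

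- Low: 0.10 × 7 / 82.6 = 0.85%.
- High: 0.30 × 42 / 82.6 = 15.3%.

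| True TMA rate | Expected cases in 24 | Missed, low | Missed, high |
|---|---|---|---|
| Historical, 7/22 | 7.64 | 0.06 | 1.16 |
| Target in 8.1, 8% | 1.92 | 0.02 | 0.29 |

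**4. Progression cut-off.** It can end ascertainment on any day, including before Day +100 when most cases appear. The documents give no progression rate, so no figure can be derived.

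**5. How much one severe case matters.** One case is 1/24 = 4.2 percentage points. One-sided P values against 6/22:

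| Severe cases in 24 | Exact binomial, 6/22 fixed | Fisher, 6/22 as a sample |
|---|---|---|
| 1 | 0.005 | 0.037 |
| 2 | 0.023 | 0.096 |
| 3 | 0.075 | 0.187 |

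The 5% boundary lies between 2 and 3 cases, or between 1 and 2, depending on the test. Under either, one case decides.

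**The case against.** **Follow-up.** One can say that 6.1.3 is a single outlying sentence, that the Abstract, 2.2, 3.5 and Table 6.1 agree, and that exams and standard labs to week 24 are marked standard of care. That makes the intent clear and the calendar loss small. It does not settle what a site does at progression, where 6.1.4 points the same way as 6.1.3. The statement that the cut-offs can only miss cases depends on 8.4.1: if replaced patients under 8.2.2 were dropped from the denominator, the observed rate need not fall.

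**Severe TMA.** A patient dying with TMA may well meet another 7.2.2 item, so only deaths without one are lost. The other differences run both ways. Requiring dialysis or intervention gives fewer cases than the historical wording; adding CNS events, pleural effusion and long admission gives more. The historical wording is also a one-sentence summary and may not be the full rule applied.

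**Power.** A reader might infer that the stated power collapses. If one or two of the six historical cases were severe by death alone, the benchmark would be 5/22 or 4/22, and exact power at a 4% trial rate would be 75% or 38%. The documents do not support this: 1.3 gives no breakdown, so the number may be zero. Holding the trial at 4% while narrowing only the benchmark is also inconsistent. Scaling the trial rate in proportion (3.3%, 2.7%) gives 81% and 52%. The 4/22 figure is partly discreteness, since P(X≤1) there is 0.0513.

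**Smaller items.** The end point in "non-relapse mortality by Day +100 and by Day +180 post-HSCT" belongs to a different outcome and does not contradict the TMA window. PRES may already fall within the CNS item in 7.2.2, whose wording is not exhaustive.

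**Conclusion.** Wrong as written, for the secondary TMA endpoints only.

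The follow-up conflict and the omission of death are plain in the text. The calendar shortfall is 7–42 days under the assumed leads, and probably costs little: at most about 1.2 missed cases in 24 even with no drug effect. The progression cut-off is probably the larger loss, of unknown size.

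For severe TMA, the omission of death taken alone lowers the trial count relative to the benchmark, and one case can change the result or leave the 8.1 trigger unfired. A reader might infer that the whole comparison is tilted toward defibrotide. That does not follow: the other definition differences act in both directions, so the net bias and any change in power stay unknown until the historical cases are re-tabulated. Confidence is high on the conflicts and low on the magnitudes.

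**What to change.** 1. **Section 6.1.3:** follow for 6 months after HSCT (tandem: after the second HSCT) or until death, with TMA ascertainment continuing after progression while consent stands. Say in 6.1.4 that withdrawal for progression does not end that ascertainment.
2. **Sections 2.2 and 7.2.2:** use one severe-TMA list. Include death with TMA, as 2.2 and the historical review do, and state whether PRES and admission over 90 days count.
3. **Historical controls:** re-tabulate the 22 high-risk patients under that list and the 6-month post-HSCT window; section 1.3 does not state the window used. Restate 7/22, 6/22 and the power in 8.1 and 8.2.1 only if they change.
4. **Optional, 8.2.2:** confirm that replaced patients who received defibrotide stay in the analysis population, as 8.4.1 already says.

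The cost is wording in four sections (five with item 4) and a second look at 22 already reviewed transplants. Scheduled exams and standard labs are already standard of care. The downside is that the observed TMA rate may be slightly higher and the stated power may change.
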